11.2. Pharmacokinetic and Pharmacodynamics Parameters Estimation

PopPK and PK/PD analyses will be conducted by a designated CRO using pre-specified models based on existing information from previous studies in adults. For efficacy, PD endpoints are defined as the 2 primary clinical efficacy endpoints of the study: PP NRS responder and IGA success. If needed, specific PK/PD analyses might be conducted for safety.

Results of PopPK and PK/PD analyses will not be included in the CSR final TFLs. PopPK and PK/PD analyses will be described in an ad hoc Modeling & Simulation Plan. PopPK and PK/PD analyses results will be described in ad hoc Modeling & Simulation Report.

11.3. Biomarkers

Blood and stratum corneum (D-Squames) samples will be collected from approximately 100 subjects at selected sites to investigate the effect of Nemolizumab (CD14152) on selected RNA and protein biomarkers, including but not limited to IL-31. Optional skin biopsies for RNA and immunohistochemistry analyses will be collected from approximately 30 subjects at selected sites who sign the additional consent form. Samples will be collected at Baseline and Week 16 and blood samples will be collected at Week 8 and Week 24 additionally.

These biomarker data will be analyzed according to a separate Analysis Plan and presented in a separate biomarkers report.

This document is confidential.

12. Immunogenicity

Blood samples to assess anti-Nemolizumab ADA will be collected at Baseline, Week 8, Week 16, Week 24 and Early Termination. Immunogenicity analyses will be summarized on the PK analysis population.

Details related to the processing of serum samples and the assessments of ADA will be described in the bioanalytical plan, which will be finalized before the beginning of sample analysis. Results will be described in the bioanalytical report, which will be included as an appendix in the final clinical study report.

Incidence of ADA results will be summarized (absolute occurrence and percent of subjects) by body weight at baseline cut-off (< 90 kg or \geq 90 kg) at each visit. The concentration of ADA titer and neutralizing antibodies will be summarized depending on the data requirement.

The number and percentage of subjects with treatment related ADA will be summarized. A treatment-related ADA is defined when the Baseline final ADA result is negative (i.e. either screening or confirmatory are negative) and the post-baseline final ADA result is positive (i.e. both screening and confirmatory are positive).

This document is confidential.

13. Safety

All safety data will be summarized and listed on the SAF population.

Safety assessments will be conducted for all subjects at the screening visit (upon signing of the ICF) and at every subsequent visit. Safety will be assessed on the basis of AEs (including TEAEs, AESIs, SAEs and adjudicated AEs), physical examination and vital signs, clinical laboratory tests, electrocardiogram (ECG), respiratory examination and assessments. Summary of all safety endpoints will be presented for each treatment group.

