2.1. Responsibilities

Syneos Health will perform the statistical analyses and is responsible for the production and quality control of all tables, figures and listings.

Descriptive summary and listing will be provided for pharmacokinetic concentration. Definition of the Pharmacokinetic analysis population and derivation of Pharmacokinetic parameters will be performed by a designated CRO. This designated CRO will be responsible for the ad-hoc Modeling / Simulation Plan and the Modeling & Simulation Report. Any analysis of pharmacokinetic parameters will not be included in the CSR final TFLs but in the dedicated Modeling & Simulation Report. For further details see [Section 11.2](#).

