6.5. Pharmacokinetic Analysis Population

The PK analysis population will consist of all subjects included in the SAF, with at least one measurable post-baseline PK assessment. Similar to SAF, the treatment group assignment in this population will be defined by the treatment actually received. This population will be used for the descriptive analyses of PK concentrations.

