8.1. General Methods

- All data will be listed, and summary tables will be provided.
- Unless otherwise specified, summaries will be presented for each treatment and overall, if indicated, by visit.
- Continuous variables will be summarized using the number of observations (n), mean, standard deviation (SD), median, 1st Quartile (Q1), 3rd Quartile (Q3), minimum, and maximum. Categorical variables will be summarized using number of observations (n), frequency and percentages of subjects in each category.
- Unless otherwise stated, all statistical tests will be two-sided and conducted at the 5% level; all presented confidence intervals (CIs) will be two-sided 95% CIs.

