9.1. Subject Disposition and Withdrawals

All subjects of the Screened population will be accounted for in this study.

Subject accounting will summarize subjects screened, re-screened, screen failed, randomized and randomized but not treated for all subjects by overall, country and site.

Subject accounting by visit will be summarized by treatment group and overall at each visit (scheduled visits only).

Subject disposition will be summarized based on the ITT population by treatment and overall. Summaries will include subjects randomized, subjects randomized but not treated, subjects treated, subjects completed treatment, subjects discontinued treatment, primary reason for discontinuation of treatment (including summary of subjects who stopped treatment due to COVID-19), subjects completed the study, subjects discontinued from the study, primary reason for discontinuation from the study (including summary of subjects who discontinued due to COVID-19), subjects rolled over to long term extension (LTE), and subjects completed Follow-up. Subjects who stopped treatment or discontinued study due to COVID-19 will be identified using other specify field in CRF.

Subject disposition will also be summarized by site on the ITT population.

Screen failure will be summarized for all screened subjects. Number of subjects screened and failed will be presented. Number and percentage of reason for screen failure (including summary of subjects who failed due to COVID-19) will be summarized.

Subjects in each analysis population (ITT, SAF, PP, PK analysis population) will be summarized by treatment group on the ITT population.

In addition, time (days since the first dose of study drug) to permanent discontinuation of study drug by reason for discontinuation will be displayed graphically in subjects having permanently discontinued from the study drug.

Randomization, study completion, drug completion, and visit dates will be listed for the ITT population. Screen failure reason will also be listed. Additional listing of missed assessment for subjects who discontinued due to COVID-19 will be presented for the ITT population.

Analysis populations will be summarized and listed on the ITT population.

All inclusion and exclusion criteria not met will be listed on the Screened population.

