9.2. Demographic and Baseline Disease Characteristics

Summary statistics for demographic and other Baseline disease characteristics will be presented for the ITT, SAF, PP and PK analysis population.

Age (years), height (cm), weight (kg), and BMI (kg/m²) will be summarized using summary statistics for continuous variables. Age groups (18-65, and > 65), sex, region (Europe and North America), race,

This document is confidential.

ethnicity, and smoking status will be summarized using the summary statistics for categorical variables. Weight will additionally be presented for each subgroup < 90 kg and \geq 90 kg.

The Baseline disease characteristics IGA, weekly average PP NRS, weekly average AP NRS, weekly average SD NRS, pain frequency and intensity, PAS item 4 (number of lesion in representative area), item 5a (excoriation/crusts), item 5b (healed lesion stages), baseline DLQI, and time since PN diagnosis will be summarized. IGA, pain frequency, PAS item 5a and 5b, and atopy background will be summarized as a categorical variable.

Atopy background (Yes, No) will be defined based on the medical history terms selected by sponsor as atopy background.

Time since PN diagnosis (months) will be defined as [date of screening – date of start of PN (MHLLT = 'Prurigo nodularis') + 1] / 30.4375.

A summary table for the stratification factor weight at randomization will be provided to show any discrepancies between what was reported through Interactive Voice Response System (IVRS)/Interactive Web Response System (IWRS) versus eCRF data (at baseline visit).

All demographic and baseline disease characteristics data will be listed on the ITT population.

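### ADA is summarized on the PK analysis population, whose entry test of a 'measurable' PK result is undefined; on one reading of the term the ADA summary has no placebo subjects

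*SAP*

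**What the plan says.** Section 12 of the SAP fixes the population for all ADA output: "Immunogenicity analyses will be summarized on the PK analysis population". Table 14.2.5.1 and Listing 16.2.6.13 carry the same label. No separate ADA-evaluable set is defined, and no ADA output on the safety population is planned.

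Section 6.5 defines the set: "The PK analysis population will consist of all subjects included in the SAF, with at least one measurable post-baseline PK assessment". It then says: "Similar to SAF, the treatment group assignment in this population will be defined by the treatment actually received". On purpose it says only: "This population will be used for the descriptive analyses of PK concentrations". ADA is not mentioned there, and the SAP nowhere says whether a BLQ result is measurable.

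Section 2.1 places the definition elsewhere: "Definition of the Pharmacokinetic analysis population and derivation of Pharmacokinetic parameters will be performed by a designated CRO".

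Three other sentences bear on who is in the set. Section 9.1: "Subjects in each analysis population (ITT, SAF, PP, PK analysis population) will be summarized by treatment group on the ITT population". Section 9.2: "Summary statistics for demographic and other Baseline disease characteristics will be presented for the ITT, SAF, PP and PK analysis population". Section 8.1: "Unless otherwise specified, summaries will be presented for each treatment and overall, if indicated, by visit". Section 12 itself names weight categories and visits for the ADA incidence, but no treatment columns.

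**The concern.** Whether a subject's ADA result is counted should depend on having an ADA result. Here it depends on a PK result, through a word that can be read in two ways.

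The reading matters for two groups.

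- **Placebo subjects.** Correctly treated placebo subjects have no nemolizumab to quantify. If measurable means quantifiable, they leave the ADA table and listing. Section 12 defines treatment-related ADA from assay results alone (negative at Baseline, positive later), so a concurrent placebo column is the direct reference for how often untreated subjects change from negative to positive. Section 3.2 words the objective as a comparison with placebo.
- **Dosed subjects with only BLQ results after Baseline.** On the same reading they also leave. Such a PK pattern may itself be linked to ADA, so the rule could remove the subjects whom an immunogenicity summary most needs to show. The SAP gives no frequency for this, and it may be small.

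Under Section 4.4, PK and ADA results are released after database lock. A term still open then could be settled with the results in hand.

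**Working it through.** **Inputs**

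- Planned size (Section 4.3): 270 randomized 2:1, 180 nemolizumab and 90 placebo.
- Ceiling of the PK set (Sections 6.4 and 6.5): the safety population, which includes dosed placebo subjects.
- Sampling times: Section 11 for PK, Section 12 for ADA, and the Schedule of Assessments (Table 4-2).

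**Step 1, the plan's own figure.** 270 × 1/3 = 90 placebo and 270 × 2/3 = 180 nemolizumab. These agree with Section 4.3.

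**Step 2, measurable means a quantifiable concentration.** The placebo count in the set is about 0, apart from any false PK signal. The planned share of randomized subjects without an ADA summary is then 90/270 = 33.3%, plus any nemolizumab subject whose post-baseline results are all BLQ.

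**Step 3, measurable means any valid result, BLQ included.** Up to 90 placebo subjects stay. Whether tying ADA to PK still loses anyone depends on the sampling times:

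| Visit | PK | ADA |
|---|---|---|
| Baseline | yes | yes |
| Week 4 | yes | no |
| Week 8 | yes | yes |
| Week 12 | yes | no |
| Week 16 | yes | yes |
| Week 24 | yes | yes |
| Week 32 follow-up | yes | no |
| Early Termination | yes | yes |
| Unscheduled, for safety | yes | yes |

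Every ADA time point has a PK sample. A subject with a post-baseline ADA result should therefore normally have a valid PK result as well; only a lost or failed PK sample would exclude them.

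**Step 4, what the placebo column gives.** If all 90 placebo subjects are kept and none is ADA-positive, the exact two-sided 95% upper limit for the background rate is 1 − 0.025^(1/90) = 0.040, or 4.0%. With no placebo subjects there is no such bound. The 4.0% is the best case for the planned size.

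**Step 5, does other text settle the word?**

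- Section 11.1 reports the number of BLQ results on the PK set. That fits both readings, because a subject with one quantifiable result can have BLQ results at other visits, including Baseline.
- Section 6.5 assigns treatment as in the safety population, Section 9.1 counts the sets by treatment group, and Section 9.2 tabulates demographics on the PK set under the by-treatment default of Section 8.1. All of this fits a set with both arms better than an active-only set.
- No sentence says that placebo subjects belong, and Section 2.1 leaves the definition to a CRO.

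**The case against.** The best defence is that the set is meant to include placebo. It starts from the safety population, and a sentence on treatment actually received would have little purpose in an active-only set. Section 12 naming weight categories does not cancel the by-treatment default of Section 8.1; Section 11.1 uses the same form for PK concentrations. On this reading the loss is close to nil, as Step 3 shows. This stands as the more likely intention, but it is an inference, and the ordinary sense of the word in a PK definition points the other way.

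Second, Section 16.2.5.2 already sets percentage denominators as subjects in the analysis set for the treatment group who have an observation. That is correct, but the rule acts only within the set and cannot bring back subjects whom the set excludes.

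Third, the CRO sentence in Section 2.1 stands in a paragraph on PK parameters and modeling, so it may mean the modeling set. Also, the bioanalytical plan is to be final before sample analysis begins. Both points weaken the worry about a late decision, but neither defines the term for the ADA table.

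Fourth, the comparison with placebo in Section 3.2 covers PK in the same clause, Section 5.5 lists only the assay, and no between-arm ADA test is planned. The objective's wording is therefore support, not proof, that a placebo column was promised.

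**Conclusion.** The point holds as a gap in the definition of the set used for ADA, with moderate confidence. The planned placebo denominator is about 0 if BLQ results do not count and up to 90 if they do. Only the first reading does real harm: it removes the placebo reference and possibly some dosed subjects whose missing exposure is related to ADA. The effect is descriptive, and no alpha-controlled result changes.

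Stronger readings that a reader might infer are not supported:

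- That the SAP excludes placebo from the ADA summary. It does not say so, and the context leans the other way.
- That the placebo denominator could fall anywhere between 0 and 90. There are two readings, and each puts it near one end.
- That the 15% dropout lowers the upper figure to 90 × 0.85 = 76.5. This is a worst case in which every dropout leaves no post-baseline result. Membership needs only one such result, PK sampling starts at Week 4, and Early Termination collects both samples.
- That a pooled ADA percentage would be distorted. Section 12 plans no pooled percentage.

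The figures assume the planned enrolment and placebo subjects who received only placebo.

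**What to change.** Before PK and ADA results are released:

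1. Summarize and list ADA on all safety-population subjects with at least one post-baseline ADA result, by treatment actually received and regardless of PK results. For treatment-related ADA, also require a Baseline ADA result. Apply this in Section 12, Table 14.2.5.1 and Listing 16.2.6.13, with nemolizumab and placebo columns within the weight categories.
2. In Section 6.5, state whether a BLQ result counts as measurable and whether placebo subjects belong to the PK set. Reconcile this with Section 2.1, so that one place defines the set used for the tables.

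The cost is one more population label, with a matching entry in Section 9.1, Table 14.1.1.6 and Listing 16.2.3.1. ADA sampling is scheduled without restriction by arm, so no new samples are needed. It must be confirmed that the bioanalytical plan, which is not part of the SAP, assays placebo samples.

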5.5. Immunogenicity Endpoints

- ADA assay (screening, confirmatory, final, titer, NAb)

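### Treatment-related ADA is defined as seroconversion only, so a titer rise in a baseline-positive subject enters no planned count

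*SAP*

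**What the plan says.** Section 12 of the SAP (Immunogenicity) announces a subject-level result: "The number and percentage of subjects with treatment related ADA will be summarized". It then gives one route into that count. The first condition is "A treatment-related ADA is defined when the Baseline final ADA result is negative". The second is "and the post-baseline final ADA result is positive (i.e. both screening and confirmatory are positive". Titer plays no part in either.

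Three other statements bear on the point:

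- Section 5.5 lists the endpoint as "ADA assay (screening, confirmatory, final, titer, NAb", so titer is one of its components.
- Section 12 on sampling: "Blood samples to assess anti-Nemolizumab ADA will be collected at Baseline, Week 8, Week 16, Week 24 and Early Termination".
- Section 12 on titer analysis: "The concentration of ADA titer and neutralizing antibodies will be summarized depending on the data requirement".

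Section 12 also plans a by-visit summary: "Incidence of ADA results will be summarized (absolute occurrence and percent of subjects", split by baseline body weight. The index of tables has one immunogenicity table (14.2.5.1) and the index of listings has one listing (16.2.6.13).

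**The concern.** The label treatment-related suggests a count of every subject whose antibody response was provoked by the drug. The definition counts only those who move from negative to positive. A subject with pre-existing antibodies whose titer climbs on treatment has also responded to the drug, but is classed with those who had no treatment-related response.

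Immunogenicity is a stated secondary objective (Section 3.2). What is at stake is whether the reported percentage of treatment-related ADA is complete. If baseline positives stay in the denominator while barred from the numerator, the percentage can err only downward as a measure of all treatment-provoked responses.

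**Working it through.** The SAP gives no figure to reproduce here. The check is a reading of the definition against the other planned outputs, followed by a simple ceiling.

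**1. Can a baseline-positive subject meet the definition?** Both conditions are required, and the first is a negative baseline final result. A baseline-positive subject fails it whatever happens later.

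**2. Are the data available to count a rise?** Titer is an endpoint component (Section 5.5), and samples are taken at baseline and post-baseline (Section 12). A within-subject comparison is possible wherever titers exist at both times.

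**3. Does another planned output count these subjects?**

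| Output | What it gives for a baseline-positive subject whose titer rises |
|---|---|
| Treatment-related ADA count | Cannot be included |
| By-visit ADA incidence | Positive at baseline and positive later; status alone does not show a rise |
| Titer and neutralizing-antibody summary | May show a shift in titers, but is conditional and has no threshold |
| Table 14.2.5.1 | The single immunogenicity summary; no boosted category is defined for it |
| Listing 16.2.6.13 | Individual results; a rise may be visible, but nothing is counted |

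**4. What is the denominator?** Section 12 states none. The default in Section 16.2.5.2 (Table Conventions) is the number of subjects in the analysis set and treatment group who have an observation, unless otherwise noted. Section 12 notes no exception, so by default baseline positives are included. The same section allows denominators to be settled in footnotes or programming notes, so this is an inference from the default.

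**5. How many subjects could be affected?** Inputs: 180 nemolizumab subjects planned (Section 4.3), and baseline positivity of 2-10%, which is an assumption because the SAP gives no rate.

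- Ineligible subjects = number in arm × baseline-positive rate
- 180 × 0.02 = 3.6, about 4
- 180 × 0.10 = 18

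This is a ceiling. The undercount is the ineligible number × the proportion who boost, and the SAP gives no boosting rate. If, purely for illustration, 10-25% of baseline positives boosted:

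- Low end: 3.6 × 0.10 = 0.36, about 0.4 subjects, or 0.36 / 180 = 0.2% of the arm
- High end: 18 × 0.25 = 4.5 subjects, or 4.5 / 180 = 2.5% of the arm

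Section 12 uses the PK analysis population, which Section 6.5 limits to treated subjects with at least one measurable post-baseline PK assessment. The base may therefore be below 180, and these figures would shrink in proportion.

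**The case against.** The best defence is that the definition is explicit, pre-specified and reproducible, and contradicts nothing else in the SAP. It is a seroconversion definition under a broader label. Immunogenicity is descriptive here, with no hypothesis test and no link to the primary or key secondary endpoints. That stands, and it limits the point to a modest improvement in reporting.

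Second, part of the subject is left to a document that is not shown: "Details related to the processing of serum samples and the assessments of ADA will be described in the bioanalytical plan". What counts as a meaningful titer rise depends on the assay and could reasonably sit there. This weakens any claim that boosting will go unassessed in the trial. It does not cure the count, because the SAP itself fixes the treatment-related definition. If the bioanalytical plan does define boosting, the two would still need aligning.

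Three stronger readings are tempting, and the SAP does not support them:

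- **Boosting is hidden.** A reader might infer this, but baseline-positive subjects appear in by-visit incidence and in the listing, and a titer summary may be made. What is missing is a count.
- **4-18 subjects are missed.** A reader might take the ceiling for the undercount. It is the number ineligible under an assumed prevalence, and only those who boost are missed.
- **Boosted responses matter most for exposure or safety.** The SAP contains nothing that shows this, nor does it supply a particular fold-rise as the correct threshold.

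**Conclusion.** The point holds as a narrow one. Section 12 sets a rule under which a baseline-positive subject with a titer rise cannot be counted as having treatment-related ADA, and no other planned output counts such subjects. This is a stated rule that can undercount, on an endpoint component that is measured but whose analysis is left conditional.

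The size is uncertain and probably small. The ceiling of about 4-18 ineligible subjects rests on the assumed 2-10% baseline positivity and on all 180 nemolizumab subjects being in the PK analysis population. If baseline positivity is near zero, the effect is negligible. The statement about the denominator rests on the general default applying, since Section 12 is silent. Efficacy conclusions are not touched.

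**What to change.** Revise Section 12 before ADA results are released. Section 4.4 places that release after database lock, so the rule can be set without sight of the data.

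- Define treatment-emergent ADA as treatment-induced (baseline negative, post-baseline positive) plus treatment-boosted (baseline positive with a titer rise above a pre-set threshold).
- Tie the threshold to the assay's variability and align it with the bioanalytical plan.
- Report induced, boosted and total counts and percentages in table 14.2.5.1, among subjects with a baseline and at least one post-baseline ADA result, and state that denominator in Section 12.
- Make the titer summary unconditional.

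The cost is one definition and a few table rows. No new samples are needed. The reported ADA rate may rise slightly.
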